**Figure RHY.6.3. Patient categories (evaluable/unevaluable) based on sample status at baseline and postbaseline.**

#### 6.13.8.1.3. Definitions for Clinical Interpretation of Assay Results

- **Baseline:** Unless otherwise specified, baseline is the last nonmissing observation on, or prior to, the date of the first injection of study treatment of ixekizumab from the originating study or RHY (that is, for patients initially randomized to ixekizumab during the originating study, the baseline will be Week 0 of the originating study; for patients randomized to placebo or adalimumab in the originating study, baseline is on or prior to the first injection of ixekizumab).
- **Baseline ADA positive (preexisting antibody):** ADA detected in a sample collected at baseline.
- **Baseline ADA-negative:** ADA is not detected in a sample collected at baseline.
- **TE-ADA positive:** a) a patient with a  $\geq 4$ -fold increase over a positive baseline antibody titer (Tier 3); or b) for a negative baseline titer, a patient with an increase from the baseline to a level of  $\geq 1:10$ .
- **TE-ADA inconclusive patient:** A patient without a TE-ADA positive sample and with at least 1 sample for which drug levels may interfere with the ADA assay.
- **TE-ADA negative patient:** A patient who is evaluable for TE-ADA and is not either TE-ADA positive or TE-ADA inconclusive.

Figure RHY.6.4 illustrates the relationship of some of these terms.

Abbreviation: ADA = anti-drug antibody.

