For safety analysis for the RW Safety Population, baseline is defined as the last nonmissing assessment prior to the first injection of study treatment in Period 2.

Fisher's exact test will be used for all adverse event (AE), discontinuation, and other categorical safety data. Continuous vital sign and laboratory values will be analyzed by an ANCOVA with treatment and baseline value in the model.

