**Figure RHBY.6.4. Relationship of terms for clinical interpretation of assay results for evaluable patients.**

- **Incidence of TE-ADA:** Patients with TE-ADA as a proportion of the evaluable patient population during the treatment period. This excludes unevaluable patients.
- **Follow-up emergent ADA:** ADA is first detected during the follow-up period, after study drug administration is discontinued. This category includes patients negative at baseline who increased to  $\geq 1:10$  titer after baseline in the follow-up period or patients ADA positive at baseline and increased at least 4-fold (2 dilutions) over baseline for the first time in the follow-up period.
- **Incidence of follow-up emergent ADA:** Patients with follow-up emergent ADA as a proportion of the follow-up evaluable patient population. This excludes unevaluable patients.

All ADA positive samples will be evaluated for NAb. Definitions for NAb patient status will be defined as follows:

- **NAb-positive patient:** A patient where a NAb positive result is detected for  $\geq 1$  TE-ADA positive samples.
- **NAb-inconclusive patient:** A patient without a NAb positive sample and with at least 1 sample for which drug levels may interfere with the NAb assay.
- **NAb-negative patient:** A patient who is evaluable for NAb and is not either NAb positive sample or NAb inconclusive.

A flow chart that reflects the connection between the analytical test results and the clinical interpretation based on the definitions is shown in [Figure RHBY.6.5](#).

[figure not shown]

Figure RHBY.6.5.

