**Table RHBY.6.10. TE-ADA Status Dichotomous Variables for AE Analysis**

TE-ADA Status Dichotomous Variable	Greater-TE-ADA Status	Lesser-TE-ADA Status
TE-ADA positive	TE-ADA positive	not TE-ADA positive
TE-ADA moderate-to-high	TE-ADA positive with moderate titer or high titer	not TE-ADA positive, or TE-ADA positive with low titer
TE-ADA high status	TE-ADA positive with high titer	not TE-ADA positive, or TE-ADA positive with low or moderate titer

Note: For purpose of this analysis, TE-ADA Inconclusive is taken to be “not TE-ADA positive.”

Note: A TE-ADA low is defined as a TE-ADA positive with a titer value  $<1:160$ ; a TE-ADA moderate is defined as a TE-ADA positive with a titer value  $\geq 1:160$  and  $<1:1,280$ ; and a TE-ADA high is defined as a TE-ADA positive with a titer value  $\geq 1:1,280$ .

For each TE-ADA status dichotomous variable, a time-varying TE-ADA status will be computed. For those time points when there is no TE-ADA sample is collected, the TE-ADA status will be derived as: at time  $t$ , the TE-ADA status is taken to be the highest of the TE-ADA values bracketing time  $t$ . More formally, the TE-ADA status at time  $t$  is given by the greater of (a) the TE-ADA status at the most-recent postbaseline measurement prior to  $t$ , and (b) the TE-ADA status at the first TE-ADA postbaseline measurement at or after time  $t$ . In this computation, “greater” is given by the greater-TE-ADA status of Table RHBY.6.10. If there is no value satisfying criterion (a), then the value (b) is used. Similarly, if there is no value (b), then the value (a) is used.

For each analysis period and each TE-ADA status dichotomous variable, patients will be categorized according to whether they were (i) always in lesser-TE-ADA status postbaseline or (ii) at least once in the greater-TE-ADA status postbaseline.

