#### **6.13.8.2.1. Analyses of Characteristics of ADA Immune Response**

The analyses of ADA effects will be conducted on all evaluable patients within the Lead-In Period Safety Population during Combined Periods 1 and 2, and Combined Periods 1, 2, and 3 and with RW Safety Population during Period 2.

Evaluable patients will be identified as positive, negative, or inconclusive for ADA, according to the definitions provided in Section [6.13.8.1.2](#).

The frequency and percentage (incidence) of patients will be summarized by treatment group for the TE-ADA status groups and the time-varying TE-ADA status groups. Scheduled visits, unscheduled visits, and repeat measurements will be included. This analysis will also be done for Group A and Group B Patients separately during Period 1.

In addition, the overall frequency and percentage (incidence) of patients will be summarized for the patients who are baseline ADA positive by TE-ADA status groups. For those patients who are TE-ADA positive, a summary of titer values and the proportion of patients who are NAb positive will also be provided.

For each TE-ADA status dichotomous variable (as defined in [Table RHBY.6.10](#)), summaries will be provided of the total postbaseline time in the greater-TE-ADA status for patients who were at some point postbaseline in the greater-TE-ADA status group. Postbaseline time in the greater-TE-ADA status for each patient will be aggregated.

A by-patient listing to include treatment, visit date, visit, ADA result, TE-ADA result, NAb result, ADA titer value, ixekizumab concentration, ADA and NAb inconclusive results will also be provided, for patients with any 1 sample of ADA (or NAb) positive or inconclusive.

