#### **6.13.8.2.3. Analyses of Treatment-Emergent ADA on Specific Adverse Events**

The analyses of TE-ADA on specific adverse events will be conducted on all evaluable patients within the Lead-In Period Safety Population during Combined Periods 1 and 2, and Combined Periods 1, 2, and 3, and for RW Safety Population during Period 2. For Lead-In Period Safety Population during the combined periods, all data are included regardless of treatment changes.

Adverse events of special interest, allergic reaction/hypersensitivity (anaphylaxis and non-anaphylaxis) and of injection-site reactions, will be included in an assessment of AE to TE-ADA over time. Timing of an AE will be taken to be the reported AE start date.

For each TE-ADA status dichotomous variable (as defined in [Table RHBY.6.10](#)), patients will be categorized according to whether they were (i) always in lesser-TE-ADA status postbaseline or (ii) at least once in greater-TE-ADA status postbaseline. For each AESI, within the time-varying TE-ADA status groups, a summary will be provided of the number of patients who had no event, events only while in lesser-TE-ADA status for group (i), or – for group (ii) – at least 1 event while in greater-TE-ADA status.

Additionally, summaries will be provided of the total number of AESI events (with unique start dates) by time-varying TE-ADA status groups at the event date. The summaries will aggregate time respectively in greater-TE-ADA status and in lesser-TE-ADA status, along with the event rates (rates per 100 patient-years) relative to those aggregate times.

By-patient listings will be provided of patients with TE-ADA who experience a treatment-emergent allergic reaction/hypersensitivity reaction or an injection site reaction.

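### Period 2 anti-drug antibody incidence by randomized arm includes antibodies that formed before randomization

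*SAP*

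**What the plan says.** SAP Section 6.13.8.1.3 gives immunogenicity its own baseline, tied to first exposure: "for patients initially randomized to ixekizumab during the originating study, the baseline will be Week 0 of the originating study", and "for patients randomized to placebo or adalimumab in the originating study, baseline is on or prior to the first injection of ixekizumab". TE-ADA positive means at least a four-fold rise over a positive baseline titer or, "for a negative baseline titer, a patient with an increase from the baseline to a level of" at least 1:10. Incidence, defined just after Figure RHBY.6.4, is "Patients with TE-ADA as a proportion of the evaluable patient population during the treatment period". Patients who were already positive when the period began are not excluded or shown separately.

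Section 6.13.8.2.1 applies these groups to the Lead-In Period Safety Population over the combined periods and also "with RW Safety Population during Period 2", summarized by treatment group.

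The time-varying status described with Table RHBY.6.10 takes, at any time without a sample, the higher of the most recent earlier postbaseline result and the next result. For each analysis period, patients are then sorted by whether they were "at least once in the greater-TE-ADA status postbaseline".

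For RW Safety analyses in general, Section 6.1.3.1 uses a later reference point: "baseline is defined as the last nonmissing assessment prior to the first injection of study treatment in Period 2". The subgroups in Section 6.14.1 show that randomized patients had 24 to 76 weeks of ixekizumab behind them (RHBX: 24-44, 52-60 or 76 weeks; RHBV and RHBW: 56-60 or 76 weeks).

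**The concern.** Everyone randomized at Week 24 had already been on ixekizumab for months. Take a patient who turned positive in the originating study or in Period 1, was randomized to placebo, and still has a titer of at least 1:10 at a Period 2 sample. Under the SAP this patient counts as TE-ADA positive on placebo in Period 2, although the antibody arose on ixekizumab. A patient of the same kind randomized to ixekizumab counts in that arm.

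The time-varying rule extends this. Because baseline precedes first exposure, the Week 24 sample is itself postbaseline. A positive Week 24 result therefore labels Period 2 time as antibody-positive up to the next sample, even if that sample is negative.

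What is at stake is the meaning of one table. A reader will take Period 2 incidence by randomized arm as what emerged after continuing or stopping the drug. It would in fact mix old and new antibodies, in proportions the table does not reveal.

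**Working it through.** **The plan's own figures.** Neither document states an antibody rate, so there is none to reproduce. The arm sizes follow from 200 randomized 2:1 (SAP Section 5.2): about 133 ixekizumab and 67 placebo. Exact enumeration of the two-sided Fisher test at flare rates of 10% and 70% gives power above 99.9%, in line with the plan's figure of over 99%.

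**Time counted before randomization.** Period 2 lasts 40 weeks. As a share of the span from antibody baseline to the end of Period 2, the pre-randomization part is 24/(24 + 40) = 37.5% for the shortest prior exposure and 76/(76 + 40) = 65.5% for the longest.

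**Effect on the reported incidence (illustration).** Assumptions, none from the documents:
- r = share TE-ADA positive before randomization: 5%, 10%, 20%
- s = share of those still positive in Period 2, equal in both arms: 50%, 100%
- q = new onset in Period 2 among the rest: 5% in one arm, 1% in the other

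Reported incidence = r × s + (1 − r) × q. For example, with r = 10% and s = 100%: 0.10 + 0.90 × 0.05 = 14.5% against 0.10 + 0.90 × 0.01 = 10.9%.

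| r | s | arm with q = 5% | arm with q = 1% | ratio | difference (points) |
|---|---|---|---|---|---|
| 5% | 100% | 9.75% | 5.95% | 1.64 | 3.8 |
| 5% | 50% | 7.25% | 3.45% | 2.10 | 3.8 |
| 10% | 100% | 14.5% | 10.9% | 1.33 | 3.6 |
| 10% | 50% | 9.5% | 5.9% | 1.61 | 3.6 |
| 20% | 100% | 24.0% | 20.8% | 1.15 | 3.2 |
| 20% | 50% | 14.0% | 10.8% | 1.30 | 3.2 |

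Counting new antibodies only, the ratio is 5.0 and the difference 4.0 points. With equal persistence the difference shrinks only by the factor (1 − r), while the ratio moves well toward 1. The share of reported positives that predate randomization, r × s divided by the reported incidence, runs from 34% to 83% in the 5% arm and from 72% to 96% in the 1% arm. With new onset of 10% and 2%, the ratio of 5.0 shows as 1.30 to 2.73.

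**Unequal persistence.** With r = 10%, new onset of 5% on ixekizumab and 1% on placebo, and persistence of 100% on ixekizumab and 50% on placebo, the table would show 14.5% against 5.9%, a difference of 8.6 points. With persistence reversed it would show 9.5% against 10.9%, or −1.4 points. The distortion then has no fixed direction.

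**Power.** With 133 and 67 patients all taken as at risk, and new onset of 5% on ixekizumab and 1% on placebo, Fisher's test has 12% power on new antibodies and 6% to 11% on the SAP's count with equal persistence. Neither count would be decisive.

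**The case against.** **The ADA rule is deliberate and specific.** This stands. A reader might infer that Sections 6.13.8.1.3 and 6.1.3.1 contradict each other. They do not: the baselines in Section 6.13 apply unless otherwise specified and name adverse events, laboratory tests and vital signs, while ADA is specified separately. Protocol Section 10.3.6.3 also describes a postbaseline sample as one taken after study drug, which fits a first-exposure baseline. That baseline is right for cumulative incidence over the combined periods. The difficulty is confined to its use for Period 2 by arm.

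**No objective depends on the comparison.** This also stands. A reader might infer that the trial sets out to test whether stopping ixekizumab raises immunogenicity. The stated objective is antibody development and its effect on efficacy at Weeks 64 and 104, and the efficacy part is analyzed in the Long-Term population (Section 6.13.8.2.2). The ADA section plans summaries and names no test.

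**Not every earlier positive counts.** True. Incidence is confined to the treatment period, so only antibodies still detectable, or carried in by the most recent earlier sample, are affected.

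**The material is already reported.** Only in part. Section 6.13.8.2.1 also summarizes Groups A and B separately in Period 1 and lists results by patient. The Period 1 summary does not divide Group B by the arm later assigned, and a listing is not a table by arm.

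**Resetting the baseline to Week 24 would bring its own bias.** This is the strongest point. At Week 24 everyone is on drug, and drug can interfere with the assay, leaving a sample inconclusive. Masked antibodies could surface as drug clears on placebo and look new in that arm only. Section 6.13.8.1.3 has no TE-ADA rule for an inconclusive baseline. This argues for a split rather than a replacement baseline.

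**Placebo time in the combined-period rates.** Section 6.13.8.2.3 says "For Lead-In Period Safety Population during the combined periods, all data are included regardless of treatment changes", and a reader might infer that this wrongly dilutes event rates. The documents do not support that. Section 6.1.1 makes the same exception for immunogenicity explicitly, and placebo injections can themselves cause site reactions. The amount is also small. If every placebo patient stayed on placebo throughout Period 2, it would be 67 × 40/52.2 = 51 of about 750 × 104/52.2 = 1,494 patient-years, or 3.4%. At the planned 70% flare rate, the 20 patients who have not flared would add at most 20 × 40/52.2 = 15 in Period 3, giving 66/1,494 = 4.4%.

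**Conclusion.** The point holds for Period 2 by randomized arm. As written, the SAP labels as treatment-emergent on ixekizumab or placebo any antibody that arose before randomization and is still detectable, or is carried in by the time-varying rule. That follows from the definitions and needs no assumed rates.

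The size does rest on assumptions. With persistence similar in the two arms, prior positives of 5% to 20% and new onset of 5% and 1%, the ratio falls from 5.0 to between 1.15 and 2.10. It is tempting to say that the arm difference is diluted as well. On these assumptions it hardly is, at 3.2 to 3.8 points instead of 4.0. If persistence differs by arm, the difference can grow or change sign.

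The consequence is a mislabelled descriptive safety table. Primary efficacy, the major secondary endpoints and the stated immunogenicity objective are untouched.

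**What to change.** In SAP Sections 6.13.8.1.3 and 6.13.8.2.1, keep the first-exposure baseline for the combined periods. For the RW Safety Population in Period 2, split TE-ADA positives by arm into:
- (a) already TE-ADA positive at the last sample before the first Period 2 injection (Week 24), without a further four-fold rise;
- (b) new, or boosted at least four-fold, after randomization.

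Show patients whose Week 24 sample is inconclusive as a separate category. State that the split is descriptive. No change is needed to the handling of placebo time in the combined-period antibody and adverse event rates.

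The cost is SAP wording and re-derivation. The Week 24 samples are already scheduled and drawn before injection (Protocol Section 2, Schedule of Activities and its footnote on immunogenicity samples). There are two downsides. Counts of new antibodies will probably be low. And antibodies masked by drug at Week 24 may become detectable on placebo as drug clears, so an excess of new positives in that arm should not be read as an effect of stopping treatment without that caveat.

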**Figure RHBY.6.4. Relationship of terms for clinical interpretation of assay results for evaluable patients.**

- **Incidence of TE-ADA:** Patients with TE-ADA as a proportion of the evaluable patient population during the treatment period. This excludes unevaluable patients.
- **Follow-up emergent ADA:** ADA is first detected during the follow-up period, after study drug administration is discontinued. This category includes patients negative at baseline who increased to  $\geq 1:10$  titer after baseline in the follow-up period or patients ADA positive at baseline and increased at least 4-fold (2 dilutions) over baseline for the first time in the follow-up period.
- **Incidence of follow-up emergent ADA:** Patients with follow-up emergent ADA as a proportion of the follow-up evaluable patient population. This excludes unevaluable patients.

All ADA positive samples will be evaluated for NAb. Definitions for NAb patient status will be defined as follows:

- **NAb-positive patient:** A patient where a NAb positive result is detected for  $\geq 1$  TE-ADA positive samples.
- **NAb-inconclusive patient:** A patient without a NAb positive sample and with at least 1 sample for which drug levels may interfere with the NAb assay.
- **NAb-negative patient:** A patient who is evaluable for NAb and is not either NAb positive sample or NAb inconclusive.

A flow chart that reflects the connection between the analytical test results and the clinical interpretation based on the definitions is shown in [Figure RHBY.6.5](#).

[figure not shown]

Figure RHBY.6.5.

**Flow chart of ADA assessment with clinical interpretation of the various result possibilities.**

### 6.13.8.2. Immunogenicity Analyses

Immunogenicity evaluable patients will be identified as TE-ADA positive, TE-ADA negative, or TE-ADA inconclusive, according to the definitions provided in Section 6.13.8.1.2 and further grouped into TE-ADA status groups and time-varying TE-ADA status groups:

#### **TE-ADA Status Groups:**

- TE-ADA status (positive, negative, or inconclusive);
- NAb status (positive, negative, or inconclusive) for TE-ADA positive patients; and
- TE-ADA titer groups for TE-ADA positive patients:
  - Low Titer: TE-ADA titer value (LOCF)  $<1:160$ ;
  - Moderate Titer: TE-ADA titer value (LOCF)  $\geq 1:160$  and  $<1:1,280$ ; and
  - High Titer: TE-ADA titer value (LOCF)  $\geq 1:1,280$ .

#### **Time-Varying TE-ADA Status Groups:**

Individual ADA samples will be ascribed into 3 different dichotomous variables as explained in Table RHBY.6.10. Each variable has possible values of a “greater-TE-ADA status” or a “lesser-TE-ADA status,” in the sense that the level of TE-ADA detected in the greater-TE-ADA category is higher than in the lesser-TE-ADA category.

**Table RHBY.6.10. TE-ADA Status Dichotomous Variables for AE Analysis**

TE-ADA Status Dichotomous Variable	Greater-TE-ADA Status	Lesser-TE-ADA Status
TE-ADA positive	TE-ADA positive	not TE-ADA positive
TE-ADA moderate-to-high	TE-ADA positive with moderate titer or high titer	not TE-ADA positive, or TE-ADA positive with low titer
TE-ADA high status	TE-ADA positive with high titer	not TE-ADA positive, or TE-ADA positive with low or moderate titer

Note: For purpose of this analysis, TE-ADA Inconclusive is taken to be “not TE-ADA positive.”

Note: A TE-ADA low is defined as a TE-ADA positive with a titer value  $<1:160$ ; a TE-ADA moderate is defined as a TE-ADA positive with a titer value  $\geq 1:160$  and  $<1:1,280$ ; and a TE-ADA high is defined as a TE-ADA positive with a titer value  $\geq 1:1,280$ .

For each TE-ADA status dichotomous variable, a time-varying TE-ADA status will be computed. For those time points when there is no TE-ADA sample is collected, the TE-ADA status will be derived as: at time  $t$ , the TE-ADA status is taken to be the highest of the TE-ADA values bracketing time  $t$ . More formally, the TE-ADA status at time  $t$  is given by the greater of (a) the TE-ADA status at the most-recent postbaseline measurement prior to  $t$ , and (b) the TE-ADA status at the first TE-ADA postbaseline measurement at or after time  $t$ . In this computation, “greater” is given by the greater-TE-ADA status of Table RHBY.6.10. If there is no value satisfying criterion (a), then the value (b) is used. Similarly, if there is no value (b), then the value (a) is used.

For each analysis period and each TE-ADA status dichotomous variable, patients will be categorized according to whether they were (i) always in lesser-TE-ADA status postbaseline or (ii) at least once in the greater-TE-ADA status postbaseline.

#### **6.13.8.2.1. Analyses of Characteristics of ADA Immune Response**

The analyses of ADA effects will be conducted on all evaluable patients within the Lead-In Period Safety Population during Combined Periods 1 and 2, and Combined Periods 1, 2, and 3 and with RW Safety Population during Period 2.

Evaluable patients will be identified as positive, negative, or inconclusive for ADA, according to the definitions provided in Section [6.13.8.1.2](#).

The frequency and percentage (incidence) of patients will be summarized by treatment group for the TE-ADA status groups and the time-varying TE-ADA status groups. Scheduled visits, unscheduled visits, and repeat measurements will be included. This analysis will also be done for Group A and Group B Patients separately during Period 1.

In addition, the overall frequency and percentage (incidence) of patients will be summarized for the patients who are baseline ADA positive by TE-ADA status groups. For those patients who are TE-ADA positive, a summary of titer values and the proportion of patients who are NAb positive will also be provided.

For each TE-ADA status dichotomous variable (as defined in [Table RHBY.6.10](#)), summaries will be provided of the total postbaseline time in the greater-TE-ADA status for patients who were at some point postbaseline in the greater-TE-ADA status group. Postbaseline time in the greater-TE-ADA status for each patient will be aggregated.

A by-patient listing to include treatment, visit date, visit, ADA result, TE-ADA result, NAb result, ADA titer value, ixekizumab concentration, ADA and NAb inconclusive results will also be provided, for patients with any 1 sample of ADA (or NAb) positive or inconclusive.

